6. STATISTICAL CONSIDERATIONS

6.1 Outcomes: The primary outcome for this Aim is *rate of HIV testing among TH clients*. Secondary outcomes will include i) *new HIV diagnoses among TH clients*, ii) *patients with +HIV test who successfully link to HIV care in 3 months*³⁰, and iii) variables that predict HIV testing. The results of this Aim are central to demonstrating feasibility for a subsequent R01 proposal.

6.2 Analysis plan: Descriptive statistics will characterize participants and summarize the data. A multi-level logistic regression model – with individual clients in level 1 nested within healers in level 2 – will be used to calculate the odds ratio for primary outcomes within three months in the intervention compared with the control arms. Adjusted analyses will be conducted as secondary or sensitivity analyses using multivariable, multi-level analyses for both binary and continuous variables. All analyses will be performed in R software.

6.3 Intervention evaluation: 3 months following enrollment, all participants will be contacted for an exit survey to understand experiences of participation in the study, undergoing HIV testing, or deciding not to test. In-depth interviews will be conducted with participating healers at the close of the intervention to obtain feedback on delivering POC testing at their practice locations and assess how the study may have impacted their beliefs and practices.

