Changes to the inclusion criteria for traditional healers were submitted as follows:

We predetermined an 8-kilometer one-way travel distance to the ISS HIV clinic as the geographic boundary within which to include traditional healers as recruitment locations for this trial. This distance was established as a walking distance to one or more HIV testing resource are centralized. Twenty-five traditional healers were identified within this area. Traditional healers will be considered eligible for participation as cluster sites if they are 1) were aged 18 years or older; 2) have a practice located within eight kilometers of the ISS clinic; 3) were identified in the 2018 population-level census of traditional healers in Mbarara District; and 4) delivered care to at least 7 patients per week. The final criterion excludes healers with average patient volumes in the lowest quartile in order to ensure that participant recruitment progresses in a timely manner for this pilot study.

Changes to the sample size were submitted as follows:

We assumed a baseline testing rate of 39% among our population based on Ministry of Health population-level data⁸. We predicted that the HIV testing rate would increase by 35% to 74% in the intervention arm. Using intracluster correlation coefficient estimate = 0.2, we calculated that we would need to include a minimum of 16 clusters total, with an average of 30 participants recruited per cluster (total sample size of 480 participants), to detect this difference, with 80% power and alpha = 0.05. We plan to recruit 20 healers as clusters in our study to maximize analytical power. Target enrollment number for clients will be 250 per study arm, divided equally among cluster sites in each study arm.

Secondary outcome of “variables that predict HIV testing” was also removed

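### Section 6.2 states no small-sample inference for a multilevel logistic odds ratio on 10 healers per arm; uncorrected tests from that model run at about 6–8% type I error against the 5% used for sizing

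*Combined protocol and SAP*

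**What the plan says.** Section 6.2 (Analysis plan) gives the whole primary analysis. After "Descriptive statistics will characterize participants and summarize the data", it specifies a multilevel logistic model with clients at level 1 and healers at level 2, which "will be used to calculate the odds ratio for primary outcomes within three months in the intervention compared with the control arms". It adds that "All analyses will be performed in R software". It names no package, estimator, test, interval method, degrees of freedom, permutation test or healer-level analysis, and no other section does.

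Sections 3.1, 5.1 and 5.2 give 10 healers per arm, and section 4.3 gives 25 clients per healer. The sample-size entry in the Summary of Changes to Protocol assumes 39% testing rising to 74%: "Using intracluster correlation coefficient estimate = 0.2", "we would need to include a minimum of 16 clusters total, with an average of 30 participants recruited per cluster", "to detect this difference, with 80% power and alpha = 0.05". It then says "We plan to recruit 20 healers as clusters in our study to maximize analytical power".

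Section 4.4 calls the aim exploratory. Section 6.1 says "The results of this Aim are central to demonstrating feasibility for a subsequent R01 proposal".

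**The concern.** Arm is assigned by healer, so the treatment contrast rests on variation between 20 healers: about 18 degrees of freedom, however many clients each healer contributes. Maximum likelihood tends to underestimate the between-healer variance with so few clusters. The usual Wald z and likelihood-ratio chi-square references then treat that estimate as if it were known. Both effects make p-values too small and intervals too narrow.

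Two things are at stake. If the true effect is nil, or the observed one is borderline, the chance of declaring a difference is above the alpha on which the trial was sized. The interval for the odds ratio, which informs the larger trial, would also overstate its precision. If the method is left unnamed, it can be chosen after the data are seen.

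**Working it through.** **1. The plan's own sample size.** Inputs from the Summary of Changes: 39%, 74%, ICC 0.2, 30 per cluster, 80% power, alpha 0.05 (two-sided assumed).
- Individually randomised n per arm, with mean rate 0.565: [1.960·√(2·0.565·0.435) + 0.842·√(0.39·0.61 + 0.74·0.26)]² / 0.35² = 30.3, rounded up to 31.
- Design effect: 1 + 29·0.2 = 6.8.
- Clusters per arm: 31·6.8/30 = 7.03, rounded up to 8. That is 16 clusters and 480 clients, as stated.

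The stated figure reproduces, so these inputs are used below with the planned 20 healers of 25.

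**2. Closed-form guide (normal theory, 20 clusters, 18 df).** Each rule is expressed as an exact t-test threshold:
- ML Wald z: 1.960·√(18/20) = 1.859, so 2·P(t18 > 1.859) = 7.9%.
- Likelihood ratio on chi-square: √{18·[exp(3.841/20) − 1]} = 1.952, giving 6.7%.
- ML Wald on t18: 2.101·√(18/20) = 1.993, giving 6.2%.
- Likelihood ratio on F(1,18), critical value 4.414: √{18·[exp(4.414/20) − 1]} = 2.108, giving 4.9%.

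**3. Simulation of the planned logistic model under no effect.** The setting is 39% in both arms, ICC 0.2 and 20 × 25. The plan does not state the scale of the ICC, so three data models were used: logit-normal with proportion-scale ICC, logit-normal with latent-scale ICC, and beta-binomial. The main runs used 40,000 trials per model, with a 20,000-trial check at finer quadrature. Separate code, using Laplace and adaptive quadrature with 8,000 trials per setting, covered logit-normal data at null rates of 39%, 56.5% and 74%. A further 5,600-trial run at 39% gave 7.1% for Wald z, 6.1% for the likelihood ratio, 4.6% for the likelihood ratio on F(1,18) and 4.7% for the healer-level test.

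| Rule at nominal 5% | Type I error, all runs |
|---|---|
| Wald z | 7.1–7.8% |
| Likelihood ratio, chi-square | 6.1–6.9% |
| Wald, t on 18 df | 5.5–6.1% |
| Likelihood ratio, F(1,18) | 4.4–5.0% |
| Healer-level t-test on 20 proportions | 4.7–5.4% |
| Parametric-bootstrap likelihood ratio (two models, 1,000 trials each, SE 0.7 points) | 5.4%, 4.8% |

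For other ICCs, Wald z gives 7.4–7.8% at 0.05–0.1, 7.3–7.7% at 0.3, and 5.7–6.0% at 0.01. The excess is small only when there is almost no clustering.

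**4. Interval coverage at 39% versus 74% (two logit-normal models).**
- Wald 95% interval for the odds ratio: 92.4–92.7%.
- Likelihood-ratio interval on chi-square: 93.7–94.0% (about 3,000 runs per model, SE 0.4 points).
- Likelihood-ratio interval on F(1,18): 95.2–95.7%.

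**5. Power at 39% versus 74%.** Simulated power is 92.5–97.3% for Wald z, 91.4–96.8% for the likelihood ratio and 88.5–95.5% for the healer-level test. The likelihood ratio on F(1,18) has power equal to the healer-level test. As an analytic check, the design effect is 1 + 24·0.2 = 5.8, the SE is √(0.4303·5.8/250) = 0.0999, and 0.35/0.0999 = 3.50. A t-test on 18 df then has 91% power.

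**The case against.** The strongest reply is that the documents show an unspecified method, not an inflated test. Section 6.2 says only that an odds ratio will be calculated, and alpha 0.05 appears only as a sample-size input. This stands in part. A reader might infer that the plan chose Wald z; it did not. The 6–8% describes what the named model usually delivers when nothing further is stated, and both common outputs miss 5%.

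The study is also a pilot, is called exploratory, already models clustering by healer, and recruits 20 clusters against a stated minimum of 16. That limits the severity. It does not remove the point, because the trial is sized on a formal test and its results are meant to support a later proposal.

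A reader might infer that the planned conclusion is unsafe. The figures do not support that. Trials significant by Wald z but not by the healer-level test make up 1.7–4.1% at 74% and under 0.1% at 90%. Nor is a larger disagreement at some smaller real effect evidence of harm: the documents give no such scenario, and rejections there are correct, so the gap is one of power. The disagreement that counts as error is under no effect, at 2.5–2.7%.

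A reader might also want an interval for the difference in testing rates. That is a separate preference about effect measure, and its absence is not a small-sample error.

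**Conclusion.** The point holds as a modest, inexpensive correction that should be made before analysis. With 20 healers and no stated small-sample method, uncorrected Wald z runs at about 7–8% and the likelihood ratio at about 6–7%. At the planned effect, the matching 95% intervals for the odds ratio cover about 92–93% and about 94%. The consequence is mainly for a null or borderline result and for the precision carried into the next trial.

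The figures assume a two-sided test, equal clusters of 25, complete outcomes and usual maximum-likelihood output. They change little across data model, null rate, fitting method and ICC from 0.05 to 0.3. Unequal clusters and loss to follow-up were not simulated.

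**What to change.** Add to section 6.2 that the p-value and 95% confidence interval for the primary odds ratio use a small-sample reference with between-healer degrees of freedom. The simplest choice that keeps the planned model and effect measure is the likelihood-ratio statistic, with its profile interval, referred to F(1,18).

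Either of these is acceptable as an alternative or supporting analysis:
- A two-sided unequal-variance t-test on the 20 healer-level testing proportions. The healer-level difference equals the client-level difference only with complete follow-up and equal cluster sizes. Its risk-difference interval covers about 94% at 90% uptake, slightly under nominal.
- A parametric bootstrap from the planned model. Its test size was checked only to within 0.7 points (SE), and its interval coverage was not computed.

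Wald with t on 18 df is only a partial correction (about 5.5–6.1%) and should not be the sole remedy.

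The cost is a sentence or two in 6.2, a few lines of R, and about 2–4 points of nominal power against Wald z (1–3 against the uncorrected likelihood ratio). About 89–95% power remains at 39% versus 74%, above the stated 80%.

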1. PROTOCOL SUMMARY

Study Summary: HIV antiretroviral therapy has the potential to dramatically decrease HIV transmission worldwide¹; yet, a barrier to ending the AIDS epidemic in low-resource settings is the fact that healthcare is largely provided by traditional or spiritual healers rather than biomedical providers²⁻⁴, and there are no strategies in place to identify HIV-infected patients among Traditional Healer patients and link them to HIV care. In order to reach the UNAIDS 90-90-90 benchmarks HIV services must reach marginalized populations in endemic regions⁵, such as in southwestern Uganda. Uganda is one of seven sub-Saharan African countries accounting for 90% of all new HIV infections in this region⁶. HIV prevalence is 7.3%, with ~1.5 million people living with HIV/AIDS and 99,000 new infections in 2014⁷. However, only 50% of sexually active Ugandans have ever tested for HIV^{8,9}. Like much of sub-Saharan Africa, the majority of Ugandans utilize traditional and faith-based healers^{10,11}. Healers are more accessible than biomedical providers in resource-poor settings. Use is driven by preference as well as accessibility: healers are considered uniquely qualified to treat afflictions believed incurable by biomedicine¹². They are respected community leaders who shape clients' utilization of HIV services⁴. Those who utilize traditional healers may present to biomedical facilities late in their illness, or not at all¹³.

Study Aim and Overall Study Design: Develop a *POC HIV testing intervention at TH locations using* a cluster randomized study design. This study will be conducted among TH clients at 10 TH practice locations, to be compared with a control group receiving usual TH care. This pilot will offer HIV testing at TH practice sites to 250 TH clients. Primary outcome for this study will be *rates of HIV testing among TH clients*. Secondary outcomes will include i) *number of new HIV diagnoses among TH clients*, ii) *socio-demographic factors that predict HIV testing*, and iii) *percentage of patients with +HIV POC test who successfully link to HIV care in 3 months*.

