3. STUDY DESIGN

3.1 Design: Previously conducted qualitative work and observational data will inform implementation of a pilot study, offering HIV testing at traditional healer locations in southwestern Uganda. No compensation will be provided for healers in the intervention or control arms of the intervention. We will follow Ugandan National protocols²⁹ to administer voluntary HIV counseling and testing at healer practices in Mbarara District. Clustering for this trial will occur at the level of healer practices. For the intervention arm, we will recruit 250 clients

from ten healer practice locations. For the control arm, we will observe 250 healer clients at ten healer locations undergoing “enhanced standard of care”, where healers will participate in a pre-trial educational session describing community HIV resources available for clients, and how to access them. Enrollment will take place from twenty traditional healer practices, over a period of four months. The follow up period will be three months. Primary outcome for this intervention *will be rates of HIV testing among TH clients (Figure).*

[figure not shown]

Figure. Approach for HIV testing pilot

select half to participate in the intervention arm (N=10); the remaining half will participate in the control arm (N=10). Healers in both study arms will keep a log of participants indicating whether HIV testing was delivered (intervention) or if the participant was referred to HIV testing (control). Many healers have little formal education and describe themselves as “illiterate”; study logbooks will be created accordingly. Research assistants will create stickers with de-identified study identification numbers for each participant. The healer will place the participant ID sticker in the log book (thereby avoiding the need to be able to write numbers); logs will show pictures for receiving point-of-care HIV testing, or not testing (in the intervention arm), or referral to the District HIV clinic for HIV testing, or not referring (for the control group). Healers will circle the corresponding picture for each participant based on the outcome of the session. Research assistants will be on site, or reachable via mobile phone, to answer any questions the healers have about record keeping or study procedures.

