4. RECRUITMENT AND ENROLLMENT

4.1 Inclusion and Exclusion Criteria: Inclusion criteria for healer clients are 1) 18 year of age or older; 2) able to provide informed consent, 3) not known to be HIV infected; 4) willing to be contacted for monthly follow up for 3 months; and 5) willing to complete an exit survey after 3 months. For the intervention (HIV testing) arm, participants must agree to receive their POC HIV test results. Exclusion criteria include being under the age of 18, incapable of giving informed consent, previously being diagnosed with HIV, being unwilling to receive HIV test results, and

unwilling to participate in the testing intervention. Participating healers are eligible to participate if they meet the UNAIDS definition of traditional healer⁸, and are willing to participate in study procedures. We will select from among healers with patient volume greater than 7 patients per week in order to ensure that participant recruitment progresses in a timely manner for this pilot study.

4.2 Informed Consent: We will obtain written informed consent from both traditional healers (N=20) and their clients (N=500) participating in this study. Participating clients must consent to providing three telephone contact numbers (self, friend, and family member), home address, and permission for the research team access to medical records from the District HIV clinic. In addition, they must consent to a home visit, if they are not reachable for follow up via phone. Healers must consent to keeping a logbook of which patients received HIV testing (intervention arm) or referred to HIV testing (control arm).

4.3 Subject Enrollment: One research assistant will be assigned to each arm of the study and will base themselves at healer practices to consecutively enroll 25 clients from each healer until we reach a sample size of N=500 (four-month enrollment period). The research assistant will assign a unique study ID number to each participant, collect demographic information, and locator information for the participant and two back up contacts. This information will be used for monthly follow-up assessments, and to deliver the exit interview.

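### With 10 healers per arm and clients enrolled after allocation, the primary model should adjust for age and sex; the gain is protection against bias, not power

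*Combined protocol and SAP*

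**What the plan says.** - **Analysis (Section 6.2).** The primary odds ratio compares the arms in a model with clients nested in healers. No covariates are listed. On adjustment the plan says only: "Adjusted analyses will be conducted as secondary or sensitivity analyses using multivariable, multi-level analyses for both binary and continuous variables". The word 'unadjusted' is not used, but no other reading of the primary model is reasonable.
- **Allocation (Section 3.1).** "Clustering for this trial will occur at the level of healer practices", with ten healers per arm. The available text shows no stratification or matching, but the sentence before the allocation statement is missing from the extracted text.
- **Order of events (Sections 4.3, 5.1, 5.2).** Healers are assigned and trained before the trial starts. One research assistant per arm, based at the practices, will then "consecutively enroll 25 clients from each healer until we reach a sample size of N=500".
- **Differences between arms (Sections 4.1, 7.2).** Only intervention clients must agree to receive their test result. Inviting a sexual partner, and enrolling the partner if eligible, is described only for the intervention arm.
- **Baseline data (Section 4.3).** The assistant will "collect demographic information, and locator information for the participant and two back up contacts". The demographic items are not listed. Age is needed for eligibility (Section 4.1) and sex for gender-matched home visits (Section 5.3), so both should be on record. Prior HIV testing is not listed as collected.

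**The concern.** Randomising healers does not by itself balance clients who are recruited later by someone who knows the arm. With 20 clusters, chance differences in client mix are also larger than in an individually randomised trial of 500. Enrolling couples in one arm only could shift sex and age in particular. If such a characteristic predicts testing, the difference goes into the primary estimate, and the plan's only safeguard is a secondary or sensitivity analysis with no stated covariates.

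**Working it through.** **Step 1. Reproduce the plan's sample size** (Summary of Changes: 39% v 74%, ICC 0.2, 30 per cluster, 80% power, alpha 0.05; two-sided assumed).

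- Per arm without clustering: [1.96·√(2·0.565·0.435) + 0.84·√(0.39·0.61 + 0.74·0.26)]² / 0.35² = 30.3, rounded up to 31.
- Design effect: 1 + 29·0.2 = 6.8.
- 31·6.8 = 210.8 per arm; 210.8/30 = 7.03 clusters, rounded up to 8 per arm. That is 16 clusters and 480 clients, as stated.

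**Step 2. The planned design** (10 healers of 25 clients per arm).

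- Design effect: 1 + 24·0.2 = 5.8.
- SE of the risk difference: √[(0.2379 + 0.1924)·5.8/250] = 0.0999.
- Power for 35 points without adjustment: about 91% (t, 18 df) or 92% (normal, pooled variance).

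**Step 3. Does adjustment buy precision?** The variance of a healer's mean is proportional to 0.2 + 0.8/25 = 0.232, so 0.2/0.232 = 86% of it lies between healers. If covariates explain a share Rw of within-healer and Rb of between-healer variance, the SE ratio is √{[0.2(1−Rb) + 0.8(1−Rw)/25]/0.232}. The documents give neither share, so these are assumptions:

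| Rw | Rb | SE | Ratio | Power (t, 18 df) |
|---|---|---|---|---|
| 0 | 0 | 0.0999 | 1.000 | 91.2% |
| 0.05 | 0 | 0.0996 | 0.997 | 91.3% |
| 0.10 | 0 | 0.0992 | 0.993 | 91.5% |
| 0.05 | 0.10 | 0.0951 | 0.952 | 93.5% |
| 0.10 | 0.30 | 0.0852 | 0.853 | 97% |

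Simulated cluster-mean comparisons at an ICC near 0.2 and the planned effect agree with the upper rows: the SD of the risk difference fell by 0–2% and power moved by under 1 point. On the log-odds scale (300 runs per scenario) the SD did not fall consistently; under the null it went from 0.469 to 0.479 and from 0.428 to 0.449.

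**Step 4. How large could chance imbalance be?** For a binary covariate with prevalence π and covariate ICC ρ, the SD of the arm difference is √[2π(1−π)(1 + 24ρ)/250]. At π = 0.5 this is 4.5 points for ρ = 0 and 10.8 points for ρ = 0.2. By simulation, with prevalence 30–50% and ρ of 0.02–0.2 (assumed), a difference of 10 points or more has probability 4–35%, compared with 1.5–2.6% without clustering.

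**Step 5. What does an imbalance do to the estimate?** The spurious risk difference is roughly the shift times (p1 − p0), where p0 and p1 are the testing probabilities without and with the characteristic. Take prevalence 40% (assumed) and an overall rate of 39%, so 0.6·p0 + 0.4·p1 = 0.39:

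- Odds ratio 1.5: p0 = 0.351, p1 = 0.448, difference 0.097. A 10-point shift gives 1.0 point and a 20-point shift 1.9 points.
- Odds ratio 3: p0 = 0.286, p1 = 0.546, difference 0.260. The same shifts give 2.6 and 5.2 points.

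If the odds ratio is read as acting within a healer, variation between healers attenuates these figures slightly; simulation gave 0.8 to 4.5 points. In each case adjustment returned the null difference to about zero, with t-based null rejection near 5%.

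**The case against.** The strongest reply is that the plan already contains adjusted analyses and fixes their rank, so swapping the primary and sensitivity roles is partly preference. A reader might infer that the team could pick whichever model looks better. Section 6.2 does not support that: it makes the covariate-free model primary. What stands open is the covariate list, and since Section 7.3 has data analysed every three months, it should be fixed before outcomes are examined.

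A reader might also infer a useful gain in power. Step 3 rules that out on the plan's own ICC: a 5–15% cut in SE needs covariates that explain 10–30% of between-healer variance, and nothing in the documents supports that.

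Nor do the documents show that demographics are strong predictors. The Section 1 outcome on "socio-demographic factors that predict HIV testing" was exploratory, and the Summary of Changes removes the predictor outcome. The odds ratios in Step 5 are therefore assumptions.

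Two further points stand. Chance imbalance is already covered by a valid cluster-level standard error, so only a systematic recruitment shift is bias in the strict sense. Consecutive enrolment is a partial safeguard against such a shift. Stratified or matched allocation cannot be excluded either, because the text before the allocation sentence is missing. It would not protect against what happens at client recruitment.

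**Conclusion.** The point holds as a low-cost improvement. The primary model has no covariates, while the recruitment process makes imbalance in age and sex foreseeable. The exposure is about 1 to 5 percentage points of spurious effect, assuming a 10–20 point shift in one measured predictor with an odds ratio of 1.5 to 3. That is small beside the planned 35 points and would not by itself create a finding of that size, but it is avoidable.

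It would go too far to say that adjustment repairs the recruitment problem. The rule that only intervention clients must accept their result selects on willingness to test, which is close to the outcome itself. Age and sex cannot correct that, and prior testing is not listed as collected. That rule needs separate attention.

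**What to change.** In Section 6.2:

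1. Make the primary estimate the two-level logistic model with arm, age and sex as recorded at enrolment, and name these covariates before outcome data are examined.
2. Keep the model without covariates as the sensitivity analysis.
3. Report a standardised risk difference from the adjusted model: average the predicted probabilities over all clients under each arm, with an interval that respects clustering by healer. This puts the result on the 39% versus 74% planning scale.

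The cost is two or three sentences. No new data are needed if age and sex are on the enrolment form, which Section 4.3 should confirm. The sample size does not change. The one drawback is that the adjusted odds ratio is conditional on the covariates and so differs in meaning from the unadjusted one; the standardised risk difference addresses this. The list should stay short with only 20 clusters.
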